7.2. Overall Study Design

The study events schedule is shown in [Table 3](#). This is a double-blinded, randomized, placebo-controlled, in-clinic, Phase 1, single-dose, IM, sequential dose-escalation study in healthy adults aged 18-55. Healthy volunteers will be assigned to 1 of 5 cohorts of Scopolamine HBT dosage groups: 0.005, 0.007, 0.011, 0.014, or 0.021 mg/kg, or receive the placebo, administered by IM injection to the anterior thigh. In each cohort, 6 to 9 subjects will receive active drug and 2 to 3 subjects will receive placebo. Each cohort will have at least 3 male and 3 female subjects enrolled among the first 8 subjects in the dosing group to ensure that at least 1 male subject and 1 female subject in each dosing group receive active drug. If nonextreme DLTs are observed in any of the cohorts, 4 additional subjects, 3 active and 1 placebo, may be added to each cohort.

On the first day of dosing for each cohort, 2 subjects will be dosed (1 active and 1 placebo). Upon review of AE data for both subjects at 24 hours post dose (± 1 hour), the PI and the medical monitor will determine if it is safe to proceed with dosing the remaining 6 of the first 8 subjects.

New subjects will not be enrolled into the next higher dosage group until at least 8 subjects in the previous cohort have completed the Day 8 follow-up visit without the occurrence of DLTs, predefined as requiring termination of the study; the Data Safety Monitoring Board (DSMB) has reviewed data and made a dose-escalation recommendation to the sponsor; and the sponsor concurs with the DSMB recommendation. The sponsor must approve dose escalation. Dose escalation cannot occur until after sponsor approval of the DSMB recommendation and notification of the investigator(s), not at the time of the DSMB recommendation. [Table 4](#) shows study events for pre dose through 36 hours post dose.

This Phase 1, GCP-compliant study is being performed to collect reliable PK data for Scopolamine HBT administered IM, as these are not found in the published literature, and to inform future studies. The goal of this study is to assess safety, tolerability, and PK, including the assessment of dose exposure proportionality, of Scopolamine HBT in the 5 cohorts.

Table 3: Study Events Schedule

Study Phase	Screening	Baseline ^a	Treatment ^a			Follow-up ^b			
Procedures	Study Day	-30 to -2	-1	1 ^c	2 (24 ± 1 h)	3 (48 ± 1 h)	4 (+ 2 days)	8 (+2 days)	30 (+ 7 days)
Informed Consent		X							
Inclusion/Exclusion		X	X	X ^d					
Medical History including Demography		X	X						
Physical or Brief Neurological Examination		X	X	X ^e		X ^e		X	
Serum Pregnancy Test		X	X					X	
Laboratory Safety Tests ^f		X	X		X	X		X	
Serology ^g		X							
Urine Drug Screen ^h		X	X					X	
Alcohol Breathalyzer Test		X	X						
Body Weight and Height/Body Mass Index		X ⁱ	X ⁱ			X ⁱ		X ⁱ	
Vital Signs ^j		X	X	X	X	X		X	
Electrocardiogram (ECG), 12-lead (supine) ^k		X	X	X	X	X		X	
Dose Administration				X					
Pharmacokinetic Assessment				X ^l	X	X			
Adverse Events				X ^m	X	X	X	X	X
Prior/Concomitant Medications		X	X	X	X	X	X	X	X
Continuous Cardiovascular Monitoring				X ⁿ	X ⁿ				
Injection Site Assessment ^o				X	X	X		X	
Injection Site: VAS ^o				X	X	X		X	
Reminder of Study Restrictions		X				X	X	X	

Table 3: Study Events Schedule (Continued)

Study Phase	Screening	Baseline ^a	Treatment ^a			Follow-up ^b		
Study Day	-30 to -2	-1	1 ^c	2 (24 ± 1 h)	3 (48 ± 1 h)	4 (+ 2 days)	8 (+2 days)	30 (+ 7 days)
Procedures								
Brief Psychiatric Rating Scale (BPRS) ^d	X	X	X		X		X	
Columbia-Suicide Severity Rating Scale (C-SSRS) ^e	X	X					X	
Richmond Agitation and Sedation Scale (RASS)				X ^r				
Structured Clinical Interview for DSM-5, Clinical Trial version (SCID-5-CT)		X ^s						
Digit Symbol Substitution Test ^t	X	X			X		X	

^a Subjects will be in clinic for the baseline and treatment days. Days 2 and 3 procedures should be performed at 24 and 48 hours (± 1 hour) post dose, respectively, except for PK samples, which should be collected as close to the specified time points as possible. Refer to [Table 4](#) for expansion of pre-dose through 36-hour post-dose activities.

^b Day 4 and Day 30 follow-up is conducted by telephone. Day 4 follow-up may be performed on Days 4-6. Day 30 follow-up may be performed on Days 30-37. Day 8 follow-up is an in-clinic visit and may be performed on Days 8-10. Note: Subjects who withdraw/are withdrawn after receiving study drug will undergo all Day 8 follow-up procedures, including pregnancy testing for females, if possible.

^c See [Table 4](#) for study events occurring pre dose through 36 hours post dose.

^d Final eligibility criteria review and completion of eligibility checklist prior to dosing.

^e Abbreviated physical examinations with changes from Day -1 (baseline) noted; Day 1 exam is prior to dosing; brief neurological assessment at 1 hour post dosing (+30 min) to evaluate alertness/level of consciousness, orientation, ability to follow commands and coordination (refer to Section [11.1.5](#) and footnote ^r below).

^f Hematology (including coagulation), serum chemistry, and urinalysis (refer to Section [11.1.9.1](#), Section [11.1.9.2](#), and Section [11.1.9.3](#), respectively, for specific tests). Fasting ≥ 8 hours at screening. Adequacy of venous access will be assessed and documented at screening.

^g Hepatitis B surface antigen, hepatitis C, HIV-1/2, and syphilis testing at screening only.

^h Urine drug screen (refer to Section [11.1.9.5](#) for specific tests).

ⁱ Body weight (kg) and height (cm; screening only) will be measured at screening and body mass index (BMI) calculated. Weight will be measured on Day -1 with BMI calculation. Day-1 weight to be used for Day 1 dose determination. Weight will be measured at Day 3 and Day 8 with no BMI calculation.

^j Systolic and diastolic blood pressure, heart rate, respiration rate, body temperature, and pulse oximetry will be performed after subject has been supine for at least 5 minutes. See [Table 4](#) for vital sign time points from pre dose through 24 hours post dose.

^k See [Table 4](#) for time points to performing ECG (supine) from pre-dose through 24 hours post-dose.

¹ See [Table 4](#) for PK sample collection time points from pre dose through 36 hours post dose. PK samples should be collected as close to the actual time point as possible (within the windows specified in [Table 8](#)); however, when multiple tests are scheduled at the same time, ECG and vital signs will be performed within 5 minutes prior to the time point, and injection site and AE assessments will be performed immediately after the PK blood draw. AEs identified prior to dosing will be considered part of the medical history. Urine PK samples will be collected prior to dosing (no earlier than 2 hours pre dose) and for 24 hours after dosing. All urine specimens will be pooled into 1 of 3 collection interval containers by the subject. See [Table 4](#) for collection intervals from pre dose through 24 hours post dose. Refer to Section [9](#) for details.

^m See [Table 4](#) for AE assessment time points from pre dose through 24 hours post dose.

ⁿ Continuous cardiovascular monitoring of ECG (3-lead) and vital signs (blood pressure (at 5-15 min intervals), heart rate, respiration rate, and pulse oximetry) from 1 hour prior to dosing through 24 hours post dose (see [Table 4](#) and Section [11.1.2](#) for details).

^o Injection site assessments: Subject will be asked to rate the maximum intensity of pain, pruritus, tingling, and numbness using the VAS. See [Table 4](#) for assessment time points from pre dose through 24 hours post dose. Immediately following the subjective assessment, an assessment of pain, tenderness, erythema, and induration at the injection site will be performed by a physician, physician assistant, or nurse.

^p See [Table 4](#) for assessment time points on Day 1. For items assessed over time (eg, items 1, 2, and 3), the period of assessment should be “over the prior week,” except for the assessments performed at 6-8 and 48 hours post dose, which should be assessed “since the prior assessment.”

^q C-SSRS will be assessed at screening, Day -1 (baseline), and Day 8.

^r RASS will be used to assess alertness/level of consciousness at 1 hour post dosing (+30 min) (see footnote ^e above), and at other times for severity if AEs of general agitation or sedation occur.

^s SCID-5-CT will be administered at Day -1 to identify the presence of any major DSM-5 Axis I or II disorder. Note: Alternates who return for dosing on another day will not have the SCID repeated.

^t The DSST will be administered at screening, baseline, 48 hours post dose, and Day 8 to detect any persistent cognitive impairment. The DSST will not be used to determine eligibility.

Table 4: Study Events Schedule – Pre Dose through 36 Hours Post Dose

Activity/Assessment	Pre Dose	Dosing = Time 0	Minutes Post-dose							Hours Post-dose									
			2	5	10	15	20	30	45	1	1.5	2	3	4	5	8	12	24	36
ECG	X			X	X	X		X	X	X	X		X		X	X	X	X	
Vital Signs	X			X	X	X		X	X	X	X		X		X	X	X	X	
Abbreviated Physical or Brief Neurological Exam ^a	X									X									
Injection Site: VAS ^b	X			X	X	X		X	X	X	X		X		X	X	X	X	
Injection Site: Physician, Physician Assistant or Nurse	X			X	X	X		X	X	X	X		X		X	X	X	X	
BPRS ^c																			6
C-SSRS																			
RASS ^d			At 1 hour post-dosing (+30 min) and as needed to assess severity only if adverse events of general agitation or sedation occur																
Final Eligibility	X																		
Eligibility Checklist	X																		
Randomization	X																		
Urine PK Samples ^e	X		0-4 h										4-12 h			12-24 h			
Blood PK Samples	X		X	X	X	X	X		X		X		X		X	X	X	X	
Safety Lab Tests																			X
Adverse Events	X		X	X	X		X	X	X	X		X		X	X	X	X		
Concomitant Medications	X		X	X	X		X	X	X	X		X		X	X	X	X		
Continuous Cardiovascular Monitoring	Begin		ECG (3-lead) and vital signs (blood pressure (5-15 min intervals), heart rate, respiration rate, and pulse oximetry)(see Section 11.1.2 for details)														End		

Error! Reference source not found. Abbreviated physical exam at pre-dose; brief neurological assessment at 1 hour post dosing (+30 min) to assess alertness, orientation, ability to follow commands and coordination (refer to Section 11.1.5 and footnote ^d below).

^b If the PI or designee determines a subject is incapable of providing valid responses on the VAS due to the neuropsychiatric effects of Scopolamine HBT, the reason(s) why the VAS assessment(s) could not be done will be documented by time point in the source.

^c BPRS will be performed at 6 (+ 2) hours post dose. The + 2-hour window is provided to allow the investigator some discretion should the assessment need to be delayed or cannot be performed. The timing may be dependent on the emergence and severity of neuropsychiatric symptoms. The reason(s) why the BPRS was delayed or could not be done will be documented in the source.

^d RASS will be employed as part of the brief neurological assessment at 1 hour post dosing (+30 min) to assess alertness/level of consciousness, and at other times if adverse events of agitation or sedation occur.

^e Record the time and estimated volume of individual voids from pre dose through 24 hours post dose. This information will assist in the assessment of urine output and hydration, and will subsequently be used to calculate the total volume of urine pooled for each PK collection interval. Refer to Section 9.1.1.3 for details.

7.3. Measures Taken to Minimize/Avoid Bias

7.3.1. Randomization

Subjects who are eligible for the study following the clinical assessments will be randomly assigned to receive Scopolamine HBT, Injection or placebo. The randomization will be balanced by using randomly permuted blocks. Randomization will be performed by coded list, provided by the study statistician, to which the pharmacist and pharmacy team will be unblinded. The pharmacist and/or pharmacy technician will prepare and document the blinded drug to be administered. The person administering the study drug will be blinded. In each cohort, 6 to 9 subjects will receive active drug and 2 to 3 subjects will receive placebo. Each cohort will have at least 3 male and 3 female subjects enrolled among the first 8 subjects in the cohort to ensure that at least 1 male subject and 1 female subject in each dosing group receive active drug.

7.3.2. Blinding

This study is double blinded. The study drugs (active and placebo) are filled in amber vials with a 1.2-mL fill volume, are clear and colorless liquids, and labeling is identical. The pharmacist and/or pharmacy technician at the clinical site will fill syringes for each study subject on dosing days to maintain the blind of the study staff. However, once a subject has been dosed with Scopolamine HBT, Injection, the study staff, including the investigators, will likely become unblinded as the CNS effects of Scopolamine HBT will be evident in the subjects, especially at the higher concentrations. Nevertheless, every effort should be made to maintain the blind, even at the higher concentrations. Study participants who become unblinded will be encouraged to maintain the confidentiality of the blind from other study staff if possible, as well as other study participants.

7.3.3. Unblinding

Unblinding of a subject should be requested only in the case of medical emergency or in the event of a serious medical condition when, in the opinion of the PI, knowledge of the investigational product is essential for the clinical management or welfare of the subject.

Whenever possible before the blind is broken, the pharmacovigilance (PVG) physician will be consulted to discuss the rationale for the request. When a request for unblinding cannot be made prior to providing emergency treatment, the PI may unblind the subject's treatment.

The clinical site pharmacist will have access to individual randomization codes and can perform emergency unblinding in the event of a medical emergency or serious medical condition upon approval of the PI.

Contact Information for Emergency Unblinding:

Any emergency unblinding of individual treatment assignments and the reason for unblinding will be clearly specified by the PI in the source documentation and reported to the [REDACTED]

[REDACTED] immediately (within 24 hours) via the telephone number or safety e-mail address below:

[REDACTED]

[REDACTED]

7.4. Investigational Product

[Table 5](#) shows a summary description of the investigational product, Scopolamine HBT, Injection and the comparator product, Scopolamine Hydrobromide Placebo.

Table 5: Investigational Products

Product Name	Scopolamine Hydrobromide Trihydrate, Injection	Scopolamine Hydrobromide Placebo
Dosage Form	Liquid	Liquid
Unit Dose	0.8 or 2.0 mg/mL	0 mg/mL
Route of Administration	IM	IM
Physical Description	Amber vial with a clear, colorless liquid of 0.8 mg/mL and 2.0 mg/mL Scopolamine HBT in 1 mM citrate buffer; 150 mM sodium chloride; and adjusted to pH 3.0 ± 0.1 with hydrochloric acid and sodium hydroxide	Amber vial with a clear, colorless liquid of citrate buffer
Manufacturer	Ology Bioservices, Inc	Ology Bioservices, Inc
Lot Number	TBD	TBD
Product Indication	Scopolamine is being developed as a muscarinic receptor antagonist (SCTID 734696004) indicated for cholinergic crisis (SCTID 8563000). Scopolamine is a muscarinic antagonist indicated for temporary relief or improvement of muscarinic effects	Comparator product

For this study, the treatments to be administered are 0.005, 0.007, 0.011, 0.014, and 0.021 mg/kg of Scopolamine HBT, depending on cohort assignment, or placebo as a one-time dose to study subjects via IM injection in the anterior thigh muscle. In each cohort, 6 to 9 subjects will receive active drug and 2 to 3 subjects will receive placebo. Each cohort will have at least 3 male and 3 female subjects enrolled among the first 8 subjects in the cohort to ensure that at least 1 male subject and 1 female subject in each cohort receive active drug.

7.4.1. Investigational Product Packaging and Labeling

The investigational product, Scopolamine HBT, Injection (0.8 mg/mL and 2.0 mg/mL, equivalent to 0.55 mg and 1.38 mg Scopolamine, respectively) and Scopolamine HBT placebo are packaged in amber, 2-mL Type I USP glass vials with 13-mm sterile serum stoppers and sealed with 13-mm blue, red, or white flip-off crimp seals, respectively. Each single-use vial contains 1.2 mL (\pm 0.2 mL).

Scopolamine HBT, Injection product components are as follows:

- Scopolamine HBT, USP
- Sterile Water for Injection
- Sodium Chloride
- Citric Acid Anhydrous
- Sodium Citrate Dihydrate
- 0.1 N Hydrochloric Acid

The Scopolamine HBT Placebo product components are as follows:

- Sterile Water for Injection
- Sodium Chloride
- Citric Acid Anhydrous
- Sodium Citrate Dihydrate
- 0.1 N Hydrochloric Acid

Examples of the investigational product vial and carton labels (0.8 mg/mL, 2.0 mg/mL, and placebo) are shown in [Figure 2](#). Please note the label text has been enlarged for legibility purposes; the actual label dimensions and font will be smaller.

Figure 2: Scopolamine HBT Injection 0.8 mg/mL and 2.0 mg/mL and Placebo Labels

0.8 mg/mL Vial Label	0.8 mg/mL Carton Label

Scopolamine Hydrobromide Trihydrate, Injection, 0.8 mg/mL (0.55 mg of Scopolamine)
 
Item Number: 10-0003825 Lot No.: XXXXX
 
Contents: 1.2 mL \pm 0.12 mL Storage: 15-25°C
 
Protect from light DOM: DDMMYY
 
CAUTION: New Drug-Limited by Federal (or United States) Law to Investigational Use
 
Manufactured by Ology Bioservices for the Surgeon General – Department of the Army
	
Scopolamine Hydrobromide Trihydrate, Injection, 0.8 mg/mL (0.55 mg of Scopolamine)
 
Item Number: 10-0003825 Lot No.: XXXXX
 
Storage: 15-25°C _____ vials in Carton
 
CAUTION: New Drug-Limited by Federal (or United States) Law to Investigational Use
 
Manufactured by Ology Bioservices, Alachua, FL for the Surgeon General – Department of the Army
 
State of Florida Prescription Drug Manufacturing License. 20313

2.0 mg/mL Vial Label	2.0 mg/mL Carton Label

Scopolamine Hydrobromide Trihydrate, Injection, 2.0 mg/mL (1.38 mg of Scopolamine)
 
Item Number: 10-0003826 Lot No.: XXXXX Contents: 1.2 mL ± 0.12 mL Storage: 15-25°C Protect from light DOM: DDMMYYYY CAUTION: New Drug-Limited by Federal (or United States) Law to Investigational Use Manufactured by Ology Bioservices for the Surgeon General – Department of the Army
	
Scopolamine Hydrobromide Trihydrate, Injection, 2.0 mg/mL (1.38 mg of Scopolamine)
 
Item Number: 10-0003826 Lot No.: XXXXX Storage: 15-25°C _____ vials in Carton CAUTION: New Drug-Limited by Federal (or United States) Law to Investigational Use Manufactured by Ology Bioservices, Alachua, FL for the Surgeon General – Department of the Army State of Florida Prescription Drug Manufacturing License. 20313

Placebo Vial Label	Placebo Carton Label

Scopolamine Hydrobromide Trihydrate Placebo
 
Item Number: 10-0003824 Lot No.: XXXXX Contents: 1.2 mL ± 0.12 mL Storage: 15-25°C Protect from light DOM: DDMMYYYY CAUTION: New Drug-Limited by Federal (or United States) Law to Investigational Use Manufactured by Ology Bioservices for the Surgeon General – Department of the Army
	
Scopolamine Hydrobromide Trihydrate Placebo
 
Item Number: 10-0003824 Lot No.: XXXXX Storage: 15-25°C _____ vials in Carton CAUTION: New Drug-Limited by Federal (or United States) Law to Investigational Use Manufactured by Ology Bioservices, Alachua, FL for the Surgeon General – Department of the Army State of Florida Prescription Drug Manufacturing License. 20313

7.4.2. Investigational Product Storage

All investigational products will be stored at 15°C-25°C and protected from light.

7.4.3. Investigational Product Preparation

No dilutions are required prior to administration of the investigational products. Dosing volumes are calculated by subject weight and drawn directly from the vial. For complete details of dose preparation and administration, refer to the pharmacy manual.

Note: For determining the clinical dosing calculations, the concentration of Scopolamine HBT (Scopolamine Hydrobromide Trihydrate, Injection 0.8 mg/mL and Scopolamine Hydrobromide Trihydrate, Injection 2.0 mg/mL) should be used.

7.4.4. Investigational Product Accountability

The sponsor's representative is responsible for distributing the investigational product to the study site. The sponsor's representative has delegated drug accountability responsibility for this product to the PI at the study site; however, the sponsor's representative has ultimate responsibility for product accountability. After the investigational product is distributed, the PI is responsible for and will maintain logs of investigational product receipt, storage, reconstitution, accountability by subject, and investigational product remaining before final disposition. The PI may delegate, in writing, this responsibility to another individual, but the PI is ultimately responsible for the investigational product and its proper storage upon receipt at the study site until it is transferred back to the sponsor's representative or designee or is destroyed, as directed

by the sponsor's representative. At the study site, the logs will be maintained in the product accountability files within the pharmacy.

All unused or partially used investigational product and empty vials will be destroyed or returned to the responsible party, as directed by the sponsor's representative at the end of the study, and as stipulated by local, state, and federal regulations.

7.5. Duration of Subject Participation

Study subject participation includes 4 days and 3 nights for the in-clinic phase. Subjects will be administered drug product on Day 1 and released on Day 3. Study staff will follow up with each subject via telephone on Day 4. Subjects will return for an in-clinic visit on Day 8, and study staff will follow up with each subject via telephone on Day 30. Total duration of subject participation in the study, including the screening period and the 30-day, post-dose telephone follow-up, may be up to 9 weeks.

7.6. Dose-adjustment Criteria

New subjects will not be enrolled into the next higher dosage group until at least 8 subjects in the previous cohort have completed the Day 8 follow-up visit without the occurrence of DLTs, and the DSMB has made a recommendation to the sponsor regarding dose escalation. The sponsor must approve the dose escalation and notify the investigator(s) before any new subjects can be enrolled. The occurrence of any DLT(s) would result in the immediate discontinuation of dosing and study enrollment, pending a review of study data by the PI, research monitor, PVG physician, the DSMB, and the sponsor.

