7.6.1. Safety Criteria for Dose Adjustment or Stopping Doses

For the purposes of determining continued dosing within a cohort or dose escalation to a subsequent planned cohort, stopping rules are based on the emergence of DLTs. Nonextreme and extreme DLTs will be considered related AEs/serious adverse events (SAEs) and will be recorded/reported as such.

Dosing of study drug and study enrollment will be halted (temporarily or permanently) as follows:

- Occurrence of any extreme DLT (dosing and enrollment to be halted immediately; PI, research monitor, PVG physician, and DSMB will review and make a recommendation to the sponsor, which will determine if dosing and enrollment may continue);
- Emergence of a specified number (see [Table 6](#)) of nonextreme DLTs among subjects in a particular dosage group (DSMB will review to determine whether dosing and enrollment may continue);
- Occurrence of an SAE not already designated as an extreme or nonextreme DLT, determined to be possibly, probably, or definitely related to the investigational product; dosing and enrollment to be halted immediately until the DSMB has completed a safety review; and

- Sponsor, DSMB, or PI's clinical judgment warrants stopping based on ongoing review of the safety profile.

The maximum tolerated dose will be the highest dose at which none of the following has been observed:

- An extreme DLT in any one subject;
- A nonextreme DLT in 2 of the first 4 subjects or in 3 subjects at any time; and
- Any SAE, not already categorized as a DLT that is considered to be possibly related, probably related, or definitely related to the study drug.

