7.6.1.3. Serious Adverse Events

In the event of an SAE that has not already been designated as a DLT but has been determined by the PI, research monitor, and PVG physician to be possibly, probably, or definitely related to the study drug, the PI is to discontinue dosing study drug and study enrollment immediately until the DSMB has completed a safety review and made a recommendation to the sponsor. The sponsor must concur with the recommendation and notify the investigator(s) before enrollment can be resumed (see Section [11.2.2](#) for SAE criteria.)

Table 6: Progression of Dosing Related to Dose-Limiting Toxicity Events

Dose-Limiting Toxicity	Number of Subjects	Action	Follow-up
Extreme DLT	1	Dosing and enrollment halted	PI, research monitor, PVG physician, and DSMB review; sponsor determines whether trial should continue
Nonextreme DLT	1 of first 4 in a cohort (or 2 in the first 8)	Dosing halted	PI, research monitor, PVG physician, and DSMB review; sponsor determines whether to increase cohort size from 8 to 12
	2 of the first 4 in a cohort (or 3 total)	Dosing and enrollment halted	PI, research monitor, PVG physician, and DSMB review; sponsor determines whether trial should continue
SAE Not Already Designated as a DLT (except unrelated)	1	Dosing and enrollment halted	DSMB to make recommendation to sponsor whether trial should continue

In summary, if any one subject has an extreme DLT, enrollment and dosing will be halted pending review by the PI, research monitor, PVG physician, and DSMB. In making its determination, the DSMB will review all relevant data and obtain additional input as needed. As a guideline to the DSMB, it is suggested that if a nonextreme DLT is observed that the DSMB consider an increase in the cohort sample size from 8 to 12 if one nonextreme DLT is observed in the first 4 subjects or 1 or 2 nonextreme DLTs are observed in the first 8 subjects and that enrollment be halted if nonextreme DLTs are observed in 2 of the first 4 subjects in a cohort or in a total of 3 subjects at any time.

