In addition to the responsibilities above, the research monitor is required to review and provide an unbiased written report for all SAEs and subject deaths to the [REDACTED] within 24 hours of his or her awareness of the event. The report provided must include, at a minimum, a brief summary of the research monitor's review of the event and event outcome, relationship of the event to the investigational product, and whether the research monitor concurs with the details of the study investigator's SAE report.

The PI (or designee) will report SAEs to the DoD research monitor. Upon receipt of an SAE report (initial or follow-up), the DoD research monitor will provide the unbiased written report using the [REDACTED] Research Monitor Report Form for each assessment. The DoD Research Monitor's report may be submitted to the [REDACTED] by the Research Monitor or the PI.

Multiple follow-up reports may be necessary for a single event, depending on when additional information becomes available. The PI (or designee) will also report all events that meet extreme and non-extreme DLT criteria, unanticipated problems, and other events with the potential to impact a subject's clinical care to the research monitor. The occurrence of any DLT(s) would result in the immediate discontinuation of dosing and study enrollment, pending a review of study data by the PI, research monitor, PVG physician, the DSMB, and the sponsor.

Medical Monitor: The medical monitor's role is separate and distinct from that of the research monitor. The medical monitor is available to serve as a resource to the clinical site and may provide consultations relating to issues such as general conduct of the study, subject eligibility, or potential protocol exceptions. The medical monitor may discuss with on-site medical staff any clinical situations that arise and provide recommendations. After the first day of dosing for each cohort, the medical monitor will review safety data with the PI to determine if it is safe to proceed with dosing the remaining subjects. The medical monitor may also perform additional tasks such as reviewing safety data listings for identification of data trends.

[REDACTED] : The [REDACTED] is responsible for the review of safety data regarding The Surgeon General, Department of the Army (TSG-DA)-sponsored products. The [REDACTED] reviews all safety events and follows them until resolution.

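### Protocol 7.6 and Section 11 halt dosing for any DLT, but Table 6 has no halting row for a single nonextreme DLT first seen in subjects 5-8, or for one in subjects 9-12 that brings the total to 1 or 2

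*Protocol*

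**What the plan says.** **Unconditional rule.** Protocol 7.6 states: "The occurrence of any DLT(s) would result in the immediate discontinuation of dosing and study enrollment", pending review by the PI, research monitor, PVG physician, DSMB and sponsor. Section 11 (research monitor) repeats the sentence. The sentence before it there says that the PI "will also report all events that meet extreme and non-extreme DLT criteria" to the research monitor, so in that place it is hard to read the rule as covering extreme DLTs only.

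**Count-based rule.** Section 7.6.1 opens its list with "Dosing of study drug and study enrollment will be halted (temporarily or permanently) as follows". For nonextreme DLTs the trigger is "Emergence of a specified number", by reference to Table 6. Section 7.6.1.2 likewise lets the incidence and severity of nonextreme DLTs decide whether dosing needs to be suspended. Table 6 (in 7.6.1.3) has two nonextreme rows:

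- "1 of first 4 in a cohort (or 2 in the first 8": dosing is halted, and the sponsor decides after review whether to go from 8 to 12 subjects.
- "2 of the first 4 in a cohort (or 3 total": dosing and enrollment are halted, and the sponsor decides after review whether the trial continues.

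**Text after Table 6.** A guideline to the DSMB suggests considering expansion to 12 if one nonextreme DLT is seen in the first 4 or "1 or 2 nonextreme DLTs are observed in the first 8 subjects". It states no halt for that case. The closing text of 7.6.1.3 then stops product administration if any of the events above occurs, without saying which events are meant. It lists FDA concurrence among the conditions for resuming.

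**SAP.** SAP 3.3.1 limits the immediate stop to extreme DLTs and SAEs not judged unrelated, says that nonextreme DLTs may lead to a halt, and repeats the two rows in SAP Table 3. SAP 6.4 restates the same counts. SAP Section 1 says that the SAP was prepared against protocol version 2.0, so it is supporting evidence only.

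**The concern.** Table 6 is what site staff and the medical monitor would consult after a DLT in a healthy volunteer. If the first nonextreme DLT of a cohort appears in the sixth subject, 7.6 says stop and Table 6 gives no action. No section says which rule takes precedence. The question is whether the next injection goes ahead before the responsible parties have reviewed the event, for a drug whose expected effects (Protocol 5.3.1.2) include delirium, hallucinations and paranoia.

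The conflict lies within the protocol and does not depend on the SAP.

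**Working it through.** **1. The plan's own figure.** SAP 3.5 uses 1 - (1 - p)^N for the chance of at least one event among N active subjects. With p = 0.235 and N = 6: 1 - 0.765^6 = 0.7996. With p = 0.182 and N = 8: 1 - 0.818^8 = 0.7995. Both match the stated 80%.

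**2. The two rules side by side.** Let x be the number of subjects with a nonextreme DLT among subjects 1-4, and y the number among subjects 5-8.

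| x | y | Table 6 | 7.6 and Section 11 |
|---|---|---|---|
| 0 | 0 | no action | no action |
| 0 | 1 | **no row met** | halt |
| 0 | 2 | first row | halt |
| 1 | 0 | first row | halt |
| 1 | 1 | first row | halt |
| 1 | 2 | second row | halt |
| 2 | any | second row | halt |

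Within the first 8, only x = 0, y = 1 has a DLT and no row.

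In expansion subjects 9-12, the only count that can still be newly met is 3 in total. A nonextreme DLT there that makes the total 1 or 2 meets no row. A total of 1 is possible because SAP 3.1 lets expansion depend on AEs in the first eight, not only on DLTs.

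**3. How often the uncovered case would arise.**

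Inputs:
- SAP 3.6 blocks: 1 active and 1 placebo in subjects 1-2; 5 active and 1 placebo in subjects 3-8.
- Assumptions: nonextreme DLTs occur independently, on active drug only, with probability p per subject. The documents give no rate; 5%, 10% and 20% are illustrative.

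The placebo in subjects 3-8 falls in positions 5-8 with probability 4/6, leaving 3 active there. It falls in positions 3-4 with probability 2/6, leaving 4 active in positions 5-8. The expected number of active subjects in positions 5-8 is (2/3)(3) + (1/3)(4) = 10/3.

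- Exactly one DLT, in subjects 5-8: (10/3) p (1 - p)^5
- Any DLT in the 8, which is when 7.6 halts: 1 - (1 - p)^6
- A nonextreme row of Table 6 met: the second minus the first

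| p | Uncovered case | Any DLT (7.6) | Table 6 row met | Uncovered share of cohorts with any DLT |
|---|---|---|---|---|
| 5% | 12.9% | 26.5% | 13.6% | 49% |
| 10% | 19.7% | 46.9% | 27.2% | 42% |
| 20% | 21.8% | 73.8% | 51.9% | 30% |

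For example, at 10%: (10/3)(0.10)(0.9^5) = 0.3333 × 0.5905 = 0.197. At the 23.5% that the SAP uses for illustration: (10/3)(0.235)(0.765^5) = 0.7833 × 0.2620 = 0.205.

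**4. What these figures do not show.** They count cohorts in which the two rules disagree, not subjects put at risk. After the first two subjects, the protocol sets no stagger for the remaining 6. If all 6 are dosed together, nobody in the first 8 is left to protect. A DLT defined by the 48-hour BPRS may also appear after everyone has been dosed.

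**The case against.** The strongest reply is that the protocol already copes. Halting is consistent with every protocol section, so cautious staff breach nothing by stopping. Section 7.6.1 lets the sponsor, DSMB or PI stop on clinical judgment. The research monitor can stop the study. The DSMB charter, which Section 11 says holds the stopping and continuation criteria, was not available and may settle the matter. All of this stands and limits the practical harm. It does not make the two rules agree.

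A second reply is that the case is covered elsewhere. The guideline under Table 6 does address a single DLT in the first 8, but only as a reason to consider expansion. The closing text of 7.6.1.3 could be read as a halt. If it covers every nonextreme DLT, however, the counts in Table 6 serve no purpose; if it covers only the Table 6 events, the gap remains.

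Three stronger readings are tempting but not supported:

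- *The protocol tells staff to carry on dosing.* No section says so. Table 6 is silent on the case.
- *The first nonextreme row leaves enrollment open because it names dosing only.* Protocol 9.1.1.1 treats enrolled as meaning dosed, and 9.1.1.2 treats eligible subjects as alternates until they are dosed. Halting dosing therefore in effect halts enrollment.
- *The differing escalation wording decides whether a cohort must expand.* Expansion is permissive, and every escalation needs a DSMB recommendation and sponsor approval. The difference is a drafting matter.

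**Conclusion.** The point holds as an internal inconsistency in the protocol's halting rule and should be fixed. Sections 7.6 and 11 require a halt for any DLT. Table 6 has no row for a single nonextreme DLT first seen in subjects 5-8, or for one in subjects 9-12 that brings the total to 1 or 2. Confidence is high on the text. It is lower on practical consequence, because of the unseen charter and the unspecified stagger.

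On the stated assumptions the subjects 5-8 case would arise in roughly one cohort in eight to one in five, so it is not a remote contingency. No sample-size or power figure changes.

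**What to change.** 1. Keep the any-DLT sentence in Protocol 7.6 and Section 11. Replace the first nonextreme row of Table 6 and SAP Table 3 with: *Any nonextreme DLT below the next row's limits (1 or 2 in total, other than 2 of the first 4), at any position including subjects 9-12: dosing and enrollment halted pending review.* Follow-up: *sponsor determines whether to resume dosing and, if the cohort is still at 8, whether to expand to 12.*
2. Align the second bullet of 7.6.1, the suspension wording in 7.6.1.2, the guideline under Table 6, SAP 3.3.1 and SAP 6.4. Check the DSMB charter against the result.
3. Say whether the FDA concurrence in the closing text of 7.6.1.3 applies to this row.
4. Minor: use one escalation-gate wording in the Synopsis, 7.2, 7.6, 9.1.1, SAP 3.1 and SAP 3.3.1. If the gate stays limited to DLTs that require termination, define these by the maximum tolerated dose list in 7.6.1: any extreme DLT; "A nonextreme DLT in 2 of the first 4 subjects or in 3 subjects at any time"; or an SAE, not already a DLT, at least possibly related to study drug.

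**Cost.** A wording amendment to the protocol and SAP and a charter check, with no extra subjects or procedures. More 8-subject cohorts would pause for review than under Table 6 alone: about 26% against 14%, 47% against 27%, and 74% against 52% at 5%, 10% and 20%. Section 7.6 already requires those pauses. They would be longer if FDA concurrence applies.
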